Patients involved in this study have lived and managed their spasticity from years to decades. This clinic evolved after the sense of hopelessness that no more could be done with the traditional botulinum toxin centred plan. This multi-pronged treatment options offers the patient the choice and option to choose the treatment option they wish to undergo based on consultation with clinicians. The DNB clinic which occurs weekly is the only such clinic in Canada. The DNB is one of the rare instances where we can demonstrate what an intervention could look like. This study is not a clinical trial; thus, no patient is “enrolled” at random in a study arm. In fact, each patient is part of the decision-making tree. Patients and families may choose to forego surgery if it is the “best” option and undergo a cryo or radiofrequency neurotomy if they prefer to not undergo anesthesia, or surgical care. Patients may choose to have no change to their care pathway. Patients that do not participate in the study will undergo the same care as those that do not. All patients have the option of trying each of the options as a step wise approach to management is a typical surgical rehabilitation strategy. This study is an assessment of change from the selected clinical interventions. Finally, the patients will be enrolled after the decision to treat with a specific intervention has been selected.

Primary Objectives:

1-Degree of changes in spasticity as assessed by Modified Ashworth Scale³² from baseline and in 1, 3, 6, 9 and 12 months after the intervention. The test will be done by the trained assistant which is not enrolled in providing medical care. It will be graded as 0 (no spasticity), 1, 1+, 2, 3 and 4 which the affect part is rigid in flexion or extension.

2-Degree of changes in range of motion of tested joints as assessed by Tardieu Scale³² from base line and in 1, 3, 6, 9 and 12 months. The maximum of passive range of motion in slow movement(V1) and degree of catch in speed (V3) and active range of motion will be measured by goniometer.

3- Upper limb function changes as assessed by DASH³⁷ questionnaire (2006). It is a self-administered questionnaire that participants will be asked to fill out at baseline and in 1, 3, 6, 9 and 12 months. Final score will be calculated based on the provided formula and will be between (0), which means patient has no difficulty at all and (100) which means the worst outcome.

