The protocol follows the same assessment and preparation as cryoneurotomy. [name] has performed thousands of these interventions to nerves. They are also percutaneous nerve procedures. The protocol is quite similar as cryoneurotomy, with the exception of the probe. Pulsed radiofrequency (PRF), a technique introduced in the 1990's³³, is known to be safe and effective on nerve structures and particularly relieving pain. It delivers an electrical field and heat bursts to targeted nerves or tissues without damaging these structures. Previous studies have used continuous radiofrequency (CRF)³⁴ exposes target nerves or tissues to a continuous electrical stimulation and ablates the structures by increasing the temperature around the RF needle-tip. PRF does not produce sufficient heat to cause structural damage. The availability of cryoneurotomy is quite limited to the lack of machines in Canada, where as radiofrequency is widely performed in hospitals and clinics all across Canada. To date our availability of time on the cryoneurotomy equipment is limited, and pulsed radiofrequency will allow for shorter waits.

Sample Size Justification. Statistical Analysis

Sample Size: N = 50

This is a pilot study. A convenience sample of 50 patients is anticipated, based on the volume of patients that has been triaged in this clinic to date. Over 100 patients have been triaged in 18 months, so it is anticipated that 50 target patients to be fully completed treatment in 18 months. At 4-6 (divided between surgical and interventional) patients per month for 12 months, this is achievable based on this clinical experience. Analysis will be individualized per patient, as each will undergo a unique procedure. Statistical analysis will address each patient stream individually. The outcome measures that will used are standard clinical and functional measures, but effect sizes are not readily available from previous studies in order to formally calculate sample size. Furthermore, this study uses an exploratory prospective cohort design, rather than a parallel group trial design, limiting the rationale for providing a sample size calculation.

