To confirm that improvements in outcomes are statistically significant a paired t-test on the difference of proportions, applicable to pre-treatment and post-treatment, will be performed. Pearson's correlation and logistic regression will also be used to determine whether any key predictors are associated with any of the outcomes at final visit. We will employ repeated measures or linear mixed (multilevel) models of change to analyze within-person trajectories in all key outcomes for the intensive repeated measures data spanning the 12-month study period. Such models derive individual parameter estimates for baseline function and change pursuant to nerve or surgical procedure, and will directly index the magnitude in improvement for each outcome (pursuant to treatment) with each individual serving as their own control (i.e., with change indexed relative to each individual's own personal baseline).

If normal distribution in the outcomes does not stand, McNemar's test and Spearman correlation will be calculated instead of paired t-test and Person's correlation, respectively.

We will rely on Island Health Statistic for this process, the data will not leave Island Health and will be analyzed through REDCap. (Statistics provided by [name], Island Health)

Inclusion Criteria:

- Adult patient \geq 18 years old, with upper extremity spasticity causing functional impairment.
- Patients that have plateaued in outcomes in which the clinical examination suggests further interventions can be trialled.
- The clinical examination, including a V1 (maximal passive stretch) and V3 (Fast catch) on upper extremity examination that demonstrates further passive or active range may be possible, versus if contracture must be managed. For example, a fistled hand that can be forced open. This includes factors such as fluctuating tone or clonus interfering with assessment.
- The patient undergoes a diagnostic nerve block to determine if there is a reducible spasticity in the muscle versus contracture.
- The patient has been offered a neuroablative procedure or surgery and has elected to undergo the procedure. The patient has consented to undergo said procedure.

Exclusion Criteria:

[figure not shown]
- Patients where no consent or Assent is obtained
- Unable attend treatment schedule

Efficacy Evaluation/Schedule/length of the study:

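### An exploratory pilot tests four unranked primary outcomes for significant improvement with no named visit, Tardieu measure, joint or error control, and with a test that does not fit the scales

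*Combined protocol and SAP*

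**What the plan says.** - **Primary Objectives, items 1-4:** Modified Ashworth, Tardieu, DASH and Goal Attainment are all primary, and none is called the lead. The Ashworth item is assessed "from baseline and in 1, 3, 6, 9 and 12 months after the intervention", and the other three follow the same schedule. The Tardieu item covers slow passive range (V1), angle of catch (V3) and active range, on whichever joints are tested. Goal Attainment has a baseline fixed at -1.
- **Sample Size Justification. Statistical Analysis:** N = 50 is a convenience sample for a pilot, and "this study uses an exploratory prospective cohort design". The section adds: "Statistical analysis will address each patient stream individually".
- **Same section, the test:** a paired t-test on a difference in proportions is to be run "To confirm that improvements in outcomes are statistically significant". Its timing is given only as "applicable to pre-treatment and post-treatment". If normality fails, "McNemar's test and Spearman correlation will be calculated instead of paired t-test".
- **Same section, the models:** "We will employ repeated measures or linear mixed (multilevel) models of change" to describe trajectories over 12 months. The choice between the two is left open and no contrast is named.
- **Streams:** the accrual sentence, "At 4-6 (divided between surgical and interventional) patients per month for 12 months", can be read as two streams. The background under Need for multidisciplinary interventions names three interventions (surgery, cryoneurotomy, tenotomy). Design Details names four procedures (neurectomy, cryoneurotomy, radiofrequency, tenotomy). The stream headings give a different three (Surgical Neurectomy, Cryoneurotomy, Pulsed radiofrequency).

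No significance level, sidedness or multiplicity rule appears.

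**The concern.** The label and the test pull in different directions. An exploratory pilot can report change without error control. A statement that improvement has been confirmed as significant cannot, unless it is fixed in advance which result carries it. Here the visit, the Tardieu measure, the joint and the stream can all be chosen once the data are in, and any of the four primaries can supply the positive result.

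The named test is a second problem. A test on proportions, and McNemar as its fallback, need a yes/no outcome before and after. Ashworth is ordinal, the Tardieu angles and DASH are numerical, and Goal Attainment is a score. No responder cut-off is defined for any of them, so that too could be set afterwards. At stake is a published claim of significant improvement for a procedure that rests on a selected comparison.

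**Working it through.** **The plan's own figure.** N = 50 rests on clinic volume: 4 × 12 = 48 to 6 × 12 = 72 patients, which contains 50. No alpha, power or effect size is attached, so there is no statistical calculation to reproduce.

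**Is a visit named for the pre/post test?** Two places come close. The phrase about the final visit belongs to the sentence on correlation and logistic regression for predictors. The twelve-month follow-up in the Efficacy Evaluation section is not linked to any test. Neither fixes the pre/post comparison.

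**Does the test fit?** McNemar compares discordant pairs in two directions. With Goal Attainment every patient starts at -1, so any cut-off puts all patients in the same category at baseline and discordance can go only one way. For the other three primaries the scale would first have to be dichotomised.

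**Size, as an illustration.** Assumptions, none of them in the documents: two-sided 5%, so 2.5% false improvement per test; no true change; one visit and one measure per outcome; four primaries.

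*Continuous tests.* With independent outcomes the formula is 1 - 0.975^k:
- One analysis, k = 4: 1 - 0.975^4 = 0.096.
- Four streams, k = 16: 1 - 0.975^16 = 0.333.

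With correlated outcomes, p is the simulated chance that at least one of four normal statistics exceeds 1.96 in the improvement direction. Over four streams with no shared patients it becomes 1 - (1 - p)^4.

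| Correlation among outcomes | One analysis (p) | Four streams |
|---|---|---|
| 0 | 9.6% | 33% |
| 0.5 | 7.8% | 28% |
| 0.7 | 6.5% | 24% |

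*Exact McNemar.* Assume that 20-60% of pairs are discordant in either direction and that outcomes are independent. The per-test chance of a false improvement is q = Σ_m Bin(m; n, d) × P(X ≥ c_m). Here X ~ Bin(m, ½), d is the discordance, and c_m is the smallest count with 2P(X ≥ c_m) ≤ 0.05.
- N = 50: q = 0.0111 to 0.0153, and 1 - (1 - q)^4 = 4.4% to 6.0%.
- Four streams of 12: q = 0.00027 to 0.00897, and 1 - (1 - q)^16 = 0.4% to 13%.

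The exact test is conservative in small samples, so it gives lower figures than the continuous tests. This calculation treats all four outcomes as if two-way discordance were possible, which is not so for Goal Attainment.

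**What the remedies cost in precision.** The 95% CI half-width in SDs of change is t(0.975, n-1)/√n: 2.010/√50 = 0.28; 2.179/√13 = 0.60; 2.201/√12 = 0.64. For Holm, the first step tests at 0.05/4 = 0.0125. By noncentral t (paired test, 80% power), the detectable change goes from 0.404 to 0.488 SD at N = 50 (ratio 1.21) and from 0.889 to 1.128 SD at n = 12 (ratio 1.27).

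**The case against.** The strongest reply is that a pilot needs no multiplicity correction and that "To confirm that improvements in outcomes are statistically significant" may be everyday language for running a significance test. The first half stands: if the p-values are descriptive, no correction is due. But the plan does not call them descriptive, and the wording sits in the same section as the exploratory label. A reader might infer that the protocol makes a formal confirmatory claim and is therefore obliged to adjust. The text does not go that far. It leaves a conflict that one sentence can settle.

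A second reply is that the mixed model is the real analysis. It may be intended so, but it is not designated primary and has no named contrast. That it already estimates change is a reason to rely on it and drop the separate test.

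A third reply is that the error rates depend on invented inputs. That is right, and they should be read only as a range. A reader might also multiply four outcomes by five visits and several streams and report a far larger error rate. The documents do not support that figure. They do not say that every visit is tested, they leave the number of streams unsettled, and they name tests that behave differently from continuous ones. The section also says that analysis is individualised per patient, which makes the number of group-level tests still less certain.

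**Conclusion.** The point holds as one of wording and pre-specification, with a misfitting test. An exploratory pilot plans a significance claim on four unranked primaries, and the visit, Tardieu measure, joint, stream definition and error rate behind it are all open.

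The size is modest in a single analysis: about 6-10% with continuous tests (outcome correlation 0.7 to 0), or 4-6% with exact McNemar at N = 50. Over four streams it is about 24-33% with continuous tests, or 0.4-13% with McNemar at 12 per stream. These figures assume two-sided 5%, no true change, one visit per outcome and streams that share no patients. Patients may in fact have more than one procedure, so streams can overlap. Selection among visits, joints or Tardieu measures would raise the figures by an amount the documents do not allow one to fix.

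**What to change.** Replace the sentence that sets up the paired t-test, and the McNemar part of the fallback sentence, with:

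> Change from baseline in each primary outcome will be estimated with an unadjusted 95% CI from the repeated-measures or mixed model, with one pre-named visit, one Tardieu measure and one pre-named target joint or muscle group per patient reported first; results are exploratory and no confirmatory claim of statistical significance will be made.

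Then:
- For Modified Ashworth, report the distribution of grade changes.
- For Goal Attainment, report follow-up scores against the fixed baseline of -1 (or the value the scoring formula assigns to it).
- List the analysis streams once, reconciling the background, Design Details, the stream headings and the accrual sentence.

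If a confirmatory claim is wanted, apply Holm at two-sided 5% over the four primaries at the named visit. Use a method suited to ordinal scores for Modified Ashworth and a one-sample comparison with -1 for Goal Attainment. State that error is not controlled across streams: applied within each of four independent streams, the chance of any error in either direction can reach 1 - 0.95^4 = 18.5%.

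**Cost.** No new data are needed. The first option gives up the significance claim, and the intervals are wide: about 0.28 SD of change either side at N = 50 and about 0.6 SD at 12-13 per stream. Under Holm the detectable effect rises by about 21% at N = 50 and 27% at n = 12 (paired-t approximation). Neither option removes the bias of an uncontrolled, unblinded design.

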4- Patients satisfaction in achieving their goals after the procedure as assessed by Goal Attainment Scale³⁸. Based on this scale participants will be asked for 3 main goals that they desire to achieve after the intervention. The baseline score will be (-1) and they will be interviewed again at 1, 3, 6, 9 and 12 months, to record how they reported their achievement. The scores of (-2), (-0.5), (0), (1) and (2) will be assigned if they feel that their condition is worse than before, better but not as good as expected, as expected, better than expected and much better than expected. All goals will be weighted equally, and final score will be calculated based on the available formula, in each session. The higher score is presenting of better outcome.

Secondary Objective:

1- Upper limb function changes as assessed by Box and Block test. Participants will be in sitting position and will be asked to move the cubes from one part to the other part in 1 minute. The test will be done in baseline and in 1, 3, 6, 9 and 12 months.

2- Changes in pain as assessed by Brief Pain Inventory Questionnaire. This is a self-administered questionnaire that will be provided for participants for filling out at baseline and in 1, 3, 6, 9 and 12 months after the intervention. The Patient will ask to answer each question by choosing a number between 0 to 10, and the final score is calculating by adding these numbers together and then divided by 4. The result will show the severity of patient pain out of 10. (0 means no pain and 10 means the worst pain that can be imagine)

3- Changes in the Hand resting position as assessed by Keenan Scale (1987)³⁶. Participants will be assessed by an independent examiner and based on available scale their hand position will be graded. Grade 1 is the minimum deformity while grade 5 is the maximum deformity which is presented by clenched fist and palmar hygiene problem. The assessment will be done at baseline and in 1, 3, 6, 9 and 12 months.

4- Changes in thumb deformity (position of thumb in relation to other fingers) as assessed by House Scale (1981)³⁵. Participants will be assessed by an independent examiner and based on available scale their thumb position will be graded between 1 to 4. Grade 1 is the minimum deformity and 4 is the maximum deformity. The assessment will be done at baseline and in 1, 3, 6, 9 and 12 months.

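### The pre/post test of proportions, its McNemar fallback and the logistic regression need yes/no outcomes, but none of the ten outcomes is yes/no and no cut-point is given

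*Combined protocol and SAP*

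**What the plan says.** All of the analysis text is in the section Sample Size Justification. Statistical Analysis of the combined protocol and SAP. It plans three things that matter here.

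- A pre/post comparison meant to confirm that improvement is significant: "a paired t-test on the difference of proportions, applicable to pre-treatment and post-treatment, will be performed". Its fallback is conditional: "If normal distribution in the outcomes does not stand", McNemar's "test and Spearman correlation will be calculated instead of paired t-test" (and Pearson's correlation).
- Pearson's correlation and logistic regression, to relate predictors to the outcomes at the final visit.
- Longitudinal models: "repeated measures or linear mixed (multilevel) models of change to analyze within-person trajectories in all key outcomes". These "will directly index the magnitude in improvement for each outcome".

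The outcomes are listed under Primary Objectives (four) and Secondary Objective (six). For Goal Attainment, the fourth primary outcome, the patient names three goals. "The baseline score will be (-1) and they will be interviewed again at 1, 3, 6, 9 and 12 months". "All goals will be weighted equally, and final score will be calculated based on the available formula, in each session".

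**The concern.** A paired t-test takes numeric differences and does not in itself need yes/no data. The words about proportions, and McNemar's test, do. Each assumes that every patient is classed as yes or no before and after treatment. Nothing in the outcome list is recorded that way, and no rule turns a grade or a score into a yes or a no. The test given the confirming role therefore cannot be run as written until someone chooses a cut, and the plan does not say who, when or where.

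The fallback is wrong on a generous reading too. McNemar's test is not what one uses when paired score differences are not normal; that is the usual place of the signed-rank test. The fallback is not remote: four outcomes are short ordinal grades, and the same section says each treatment stream is analysed separately, so the samples will be smaller than 50.

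At stake is a loss of information in the named significance test and, for one primary outcome, a p-value that does not measure what it appears to measure.

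**Working it through.** **Step 1. Data type of each outcome** (Primary Objectives and Secondary Objective).

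| Outcome | Type | Yes/no? | Cut-point given? |
|---|---|---|---|
| Modified Ashworth | ordinal, 6 grades | no | no |
| Tardieu and range of motion | degrees | no | no |
| DASH | score 0-100 | no | no |
| Goal Attainment | combined multi-level score | no | no |
| Box and Block | count | no | no |
| Brief Pain Inventory | score 0-10 | no | no |
| Keenan hand position | ordinal, 1-5 | no | no |
| House thumb | ordinal, 1-4 | no | no |
| House function | ordinal, 0-8 | no | no |
| Grip strength | kg | no | no |

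Yes/no outcomes: 0 of 4 + 6 = 10. Cut-points: 0. The pre/post test of proportions, McNemar's test and the logistic regression all lack the variable they need.

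**Step 2. Goal Attainment.** With equal weights and every goal at -1 at baseline, all patients share one baseline score. McNemar's test compares b (patients crossing a cut upwards) with c (crossing downwards). With a cut above the baseline value, nobody starts above it, so c = 0 always. With a cut at or below the baseline value, nobody starts below it, so b = 0 always. The test computes, but it never sets gains against losses. With c = 0 the exact two-sided p is 2 × 0.5^b: b = 5 gives 0.0625 and b = 6 gives 0.031.

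Two constructed cases use only the follow-up levels the plan lists (-2, -0.5, 0, 1, 2). They assume that the combined score is the mean of the three goals, that each patient rates all three goals alike, and that the cut is 0.

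- All 50 patients rate their goals -0.5 ("better but not as good as expected"). Every patient has improved on -1, yet b = c = 0 and p = 1.
- Six patients reach 0 and 44 fall to -2. Mean change = (6 × 1 + 44 × (-1)) / 50 = -0.76, yet b = 6, c = 0 and p = 0.031 in the direction of gain.

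These show the misuse; they are not forecasts.

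**Step 3. Cost of dichotomising.** There is no power figure in the plan to reproduce: 50 is a convenience sample with no effect size, SD or alpha. The inputs are therefore assumptions: normal scores with SD 1 at both times, pre/post correlation r = 0.6, two-sided 5%, cut midway between the two means. Sizes are n = 50, and n = 12 for one stream (50 / 4 = 12.5 if four procedure streams were equal; the plan gives no stream sizes).

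Paired t: standardised change = δ / √(2(1 - r)). For δ = 0.4 this is 0.4 / √0.8 = 0.447, and 0.447 × √50 = 3.16, giving power of about 0.87.

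McNemar, δ = 0.4: P(below the cut before) = Φ(0.2) = 0.579, P(below it after) = Φ(-0.2) = 0.421, P(below both times) = 0.340. Crossing up: 0.579 - 0.340 = 0.239; crossing down: 0.421 - 0.340 = 0.081. Of 50 patients, about 12 and 4 count, so about 34 contribute nothing.

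Simulated power, 20,000 runs per scenario (the small ranges are differences between repeat runs and, for the signed-rank test at n = 12, may also reflect how its p-value is computed):

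| n, change | paired t | signed-rank | McNemar exact | McNemar asymptotic |
|---|---|---|---|---|
| 50, 0.4 SD | 0.87 | 0.86 | 0.43-0.44 | 0.52-0.53 |
| 12, 0.8 SD | 0.80-0.81 | 0.74-0.76 | 0.16 | 0.44-0.46 |
| 50, 0.8 SD | 1.00 | 1.00 | 0.96-0.97 | 0.98 |

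The asymptotic version has no continuity correction. At n = 12 the exact test needs at least six discordant pairs to reach 5%, and fewer than five are expected: 12 × (0.350 + 0.039) = 4.7.

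Over r = 0.4 to 0.8:

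- n = 50, 0.4 SD: paired t 0.71-0.99, exact 0.36-0.56, asymptotic 0.45-0.65.
- n = 12, 0.8 SD: paired t 0.63-0.98, exact 0.14-0.16, asymptotic 0.38-0.51.

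**The case against.** The best defence is that proportions is a slip of the pen. A normality condition makes sense only for scores, and so does the Pearson/Spearman pair. On that reading the paired t-test is sound. This is plausible, but it rescues only half of the rule: McNemar's test remains the wrong substitute. The opposite reading is also open. Proportions, McNemar's test and logistic regression together fit a responder outcome that the authors had in mind and did not write down. Then the repair is to state the definition. Either way the text has to change.

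Second, the power figures use normal scores, whereas McNemar's test is called only when scores are not normal. That stands. The figures show what is lost by cutting a score in two; they do not give the power of the fallback in the situation that triggers it.

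Third, the mixed models in the same section use the scores as they are, and this is an exploratory pilot. That also stands, and it limits the weight of the point. A reader might infer that the study is left without a valid analysis of its outcomes; the text on the mixed models shows otherwise.

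A reader might also infer that cuts would be tried until one gave a significant result, inflating false positives. Nothing in the documents suggests such selection. The gap is that no cut is stated.

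**Conclusion.** The pre/post rule is wrong as written. No outcome can enter a test of paired proportions, McNemar's test or the logistic regression without a cut-point that the plan does not give, and reading proportions as scores does not save the McNemar fallback. That conclusion needs no assumption beyond the outcome list. It rests on the text available for review.

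For Goal Attainment, McNemar's test is one-directional and misleading at any cut. It would be too strong to say that it cannot be computed.

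The size of the loss rests wholly on assumed inputs. It is large for a moderate change in 50 patients or a large change in about 12, and small for a large change in 50. The mixed models are untouched. It would be a further step to say that the plan must also rank the mixed model against the paired test or name one follow-up visit as decisive; those are separate questions and this point does not depend on them. This should be fixed before analysis, and it is not a failure of the design.

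**What to change.** In the statistical analysis section:

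1. Remove the reference to a difference of proportions and remove McNemar's test as the fallback.
2. Specify a paired t-test on within-patient score differences, with the Wilcoxon signed-rank test when those differences are not normal.
3. For the ordinal grades (Modified Ashworth, Keenan, both House scales), name a signed-rank or ordinal method in advance.
4. For Goal Attainment, the same rule amounts to testing each patient's combined score against its fixed baseline value. Do not use McNemar's test for it.
5. Keep McNemar's test (for the other outcomes) and logistic regression only if a responder definition is written down before the data are seen. If a responder outcome was intended all along, state it now.
6. Leave the planned mixed models in place.

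The cost is a few sentences. No new data and no extra patients are needed.
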